7.4 Statistical Analyses for Safety

General Considerations

Safety analyses will be carried out using the Safety Analysis Set. Safety will be assessed by AEs, lab values, vital sign measurements, ECG, clinically significant MRI abnormalities and C-SSRS. For continuous safety outcomes, the change from Baseline will be analyzed in a descriptive manner by treatment group and by visit. For categorical safety outcomes, the number and percentage of each

category will be summarized by treatment group and by visit. Shift of laboratory values from Baseline to defined time points will be tabulated. Hypothesis testing will not be performed for safety parameters.

Analysis of Adverse Events

All AEs will be coded using the current version of the Medical Dictionary for Regulatory Activities (MedDRA). The number and percentage of subjects with treatment-emergent AEs, treatment-emergent SAEs, AEs with a reasonable possibility of being related to study drug, AEs leading to study drug discontinuation will be summarized by treatment group and will be tabulated using primary MedDRA system organ class (SOC) and preferred term (PT). Treatment emergent AEs will be defined as all events that begin or worsen on or after first dose of study drug.

Analysis of Laboratory Data

Changes from Baseline in continuous laboratory parameters will be summarized by n, mean, standard deviation, minimum value, median, and maximum value for each treatment group and all subjects overall for each continuous hematology, chemistry, and urinalysis variable.

Laboratory observations will be categorized as normal, low, or high relative to the reference (normal) range associated with the laboratory that performed the assay. For each hematology, chemistry and urinalysis with a reference range, shift tables will be prepared for shifts from baseline to lowest, highest and final value during the entire study for each treatment group and all subjects overall.

Analysis of Vital Signs

Change from baseline to each planned visit and to the minimum, maximum and final value during the Treatment Period will be summarized in a descriptive manner for each treatment group and all subjects overall for each vital sign and weight. For each variable, a summary of the number and percentage of subjects who have at least one post-baseline observation that meets the potentially clinically significant (PCS) criteria and is more extreme than their baseline value will be provided for each treatment group and all subjects overall.

Other Safety Analysis

Further details and additional safety analyses will be specified in the SAP.

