5 STUDY ACTIVITIES

5.1 Eligibility Criteria

Subjects must meet all of the following criteria in order to be included in the study.

Consent

- 1. Subjects or their legally authorized representative must voluntarily provide informed consent before the initiation of any study-specific procedure in a form approved by an independent ethics committee (IEC)/institutional review board (IRB). In the absence of subject's ability to provide informed consent, informed consent must be given by a person who has the legal right to act on behalf of the subject in accordance with local laws.

Demographic Assessments

- 2. Adult male or female, 30 to 90 years of age, inclusive.
- 3. Able to be randomized within 24 hours of last known normal.
- 4. Subjects and caregivers (if applicable) are willing and able to comply with procedures required in this protocol.
- 5. In the opinion of the investigator, subject is likely to be available for follow up for the duration of the study (e.g., stable residential address).

Stroke Diagnosis

- 6. Clinical diagnosis of acute ischemic stroke supported by acute brain computed tomography (CT) or MRI consistent with the clinical diagnosis.
 - Evidence of infarct within anterior circulation based on either clinical assessment and/or acute imaging.
 - Subjects who undergo MRI as part of standard of care must have evidence of an infarct diameter ≥ 2 cm, as measured by diffusion-weighted imaging (DWI).
 - No evidence of severe stroke on imaging based on available acute imaging studies performed under the standard of care, defined by either:
 - Alberta Stroke Program Early CT Score (ASPECTS) of 0 to 4 based on CT, or
 - Acute infarct volume on MRI DWI ≥ 70 mL (for subjects who undergo as part of standard of care MRI).
 - No evidence of isolated lacunar infarct (i.e., lacunar syndrome), or isolated brainstem, or cerebellar stroke based on clinical assessment and available acute imaging studies performed under the standard of care.

- No evidence of acute intracranial hemorrhage (e.g., intracerebral hemorrhage, subarachnoid hemorrhage) on acute brain CT or MRI performed under the standard of care. Petechial hemorrhages of \leq 1 cm are allowed.

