2.2 Study Design Overview

[figure not shown]
This is a 52-week, Phase 2a, randomized, double-blind, parallel-group, placebo-controlled, multicenter proof-of concept study to evaluate the safety and efficacy of elezanumab in subjects with acute ischemic stroke.

Administration of blinded study drug must be initiated as soon as possible but no later than 6 hours after randomization and done every 4 weeks thereafter through Week 48 for a total of 13 doses. The final double-blind Treatment Period study visit will be at Week 52. Subjects will have 2 post-treatment follow-up visits at 12 and 24 weeks after last dose of study drug, and a final follow-up phone call 39 weeks (~5 half-lives) after last dose of study drug.

Final efficacy analyses will be performed after the last subject completes the Week 52 visit and after an interim database lock. Final safety analyses will be performed following completion of the post-treatment period and final database lock.

The schematic of the study is shown in [Figure 1](#).

Figure 1. Study Schematic

EVT endovascular therapy; hr(s) hour(s); IV intravenous; LKN last known normal; tPA tissue plasminogen activator; Wk week

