9.0 Safety Analyses

9.1 General Considerations

Safety data will be summarized for the Safety Analysis Set as described in Section [4.0](#). Safety summaries will be presented by treatment group.

"Baseline" refers to the last non-missing observation before the first administration of study drug.

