9.4 Analysis of Vital Signs and Weight

Vital sign measurements of systolic and diastolic blood pressure, pulse rate, and body temperature, as well as weight will be summarized.

Each vital sign variable will be summarized for all time points (starting with Baseline) for the pre-infusion value with the number of non-missing observations, mean and standard deviation, median, minimum and maximum.

Mean change from baseline to each applicable post-baseline visit based on the pre-infusion value will be summarized for each vital sign variable, with the number of observations, baseline mean, and visit mean. The change from baseline mean, standard error, and 95% confidence interval will be presented within each treatment group and between treatment group difference (elezanumab vs. placebo) based on an ANCOVA with baseline as a covariate and treatment as a main effect.

The pre-infusion and post-infusion means will be calculated for each infusion visit (time point) for subjects who have both values. The change from pre-infusion to post-infusion mean, standard error, and 95% confidence interval will be presented for within each treatment group and between treatment groups (elezanumab vs. placebo) based on an ANCOVA with baseline as a covariate and treatment as a main effect.

Vital sign variables will be evaluated based on potentially clinically significant (PCS) criteria ([Appendix C](#)). For each vital sign PCS criterion, the number and percentage of subjects who have a vital sign value meeting the criteria will be summarized. Listings will be provided to summarize subject-level vital sign data for subjects meeting PCS criteria.

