Appendix C. Potentially Clinically Significant Criteria for Safety Endpoints

The criteria for Potentially Clinically Significant (PCS) laboratory findings are described in Table C-1, and the PCS criteria for vital sign findings are described in Table C-2.

Table C-1. Criteria for Potentially Clinically Significant Hematology, Chemistry Values

Variable Measured	Potentially Clinically Significant (PCS) Criteria	
	Very Low	Very High
Hematology		
Activated partial thromboplastin time prolonged (aPTT)	NA	> ULN
Hemoglobin	< 10.0 g/dL (6.2 mmol/L, 100 g/L)	> 4 gm/dL above ULN
INR	NA	> ULN
Lymphocyte count	< 500/mm ³ (0.5 × 10 ⁹ /L)	> 20,000/mm ³
Neutrophil count	< 1000/mm ³ (1.0 × 10 ⁹ /L)	NA
Platelet count	< 75,000/mm ³ (75.0 × 10 ⁹ /L)	NA
White blood cell (WBC)	< 2000/mm ³ (2.0 × 10 ⁹ /L)	> 100,000/mm ³
Chemistry		
Blood bilirubin	NA	> 1.5 × ULN
Cholesterol	NA	> 500 mg/dL (12.92 mmol/L)
Creatinine	NA	> 1.5 × ULN
Corrected Serum Calcium	< 7.0 mg/dL (1.75 mmol/L)	> 12.5 mg/dL (3.1 mmol/L)
Glucose	< 40 mg/dL (2.2 mmol/L)	> 250 mg/dL (13.9 mmol/L)
Gamma-glutamyl Transferase	NA	> 2.5 × ULN
Potassium	< 3.0 mmol/L	> 6.0 mmol/L
Sodium	< 130 mmol/L	> 155 mmol/L
Triglycerides	NA	> 500 mg/dL (5.7 mmol/L)
Uric acid	NA	> 10 mg/dL (0.59 mmol/L)
Albumin	< 2 g/dL (20 g/L)	NA
Phosphate	< 2.0 mg/dL (0.6 mmol/L)	NA
Enzymes		
Alanine aminotransferase (ALT)	NA	> 3.0 × ULN
Alkaline phosphatase	NA	> 2.5 × ULN
Aspartate aminotransferase (AST)	NA	> 3.0 × ULN
CPK	NA	> 5.0 × ULN

Note: A post baseline value must be more extreme than the baseline value to be considered a potentially clinically significant finding.

Table C-2. Criteria for Potentially Clinically Significant Vital Sign Values

Vital Signs Variables	Criterion	Potentially Clinically Significant (PCS) Value
Systolic blood pressure (mmHg)	Low	≤ 90 mm Hg and decrease ≥ 20 mm Hg from Baseline
	High	≥ 180 mm Hg and increase ≥ 20 mm Hg from Baseline
Diastolic blood pressure (mmHg)	Low	≤ 50 mm Hg and decrease ≥ 15 mm Hg from Baseline
	High	≥ 105 mm Hg and increase ≥ 15 mm Hg from Baseline
Heart rate (bpm)	Low	≤ 50 bpm and decrease ≥ 15 bpm from Baseline
	High	≥ 120 bpm and increase ≥ 15 bpm from Baseline
Temperature	High	$\geq 38.3^{\circ}\text{C}$ and $\geq 1.1^{\circ}\text{C}$ above baseline value
Post-infusion systolic blood pressure	High	> 160 mm Hg systolic and > 20 mm Hg above pre-infusion value
Post-infusion diastolic blood pressure	High	> 105 mm Hg diastolic and > 15 mm Hg above pre-infusion value

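### SAP Table C-2 judges high systolic pressure against an acute-phase baseline, so for baselines above 160 mmHg some later readings of 180 or more are neither counted nor listed

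*Protocol*

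**What the plan says.** - Criterion: SAP Appendix C, Table C-2, flags high systolic pressure at "≥ 180 mm Hg and increase ≥ 20 mm Hg from Baseline".
- Counting and listing: under SAP 9.4, for each vital-sign criterion, "the number and percentage of subjects who have a vital sign value meeting the criteria will be summarized". Subject-level listings cover the subjects who meet the criteria.
- Protocol 7.4: the count is of subjects with "at least one post-baseline observation that meets the potentially clinically significant (PCS) criteria and is more extreme than their baseline value".
- Reference value: SAP 9.1 says that Baseline "refers to the last non-missing observation before the first administration of study drug".
- Timing: Protocol 5.1 requires subjects to be "Able to be randomized within 24 hours of last known normal". SAP 2.2 has the first dose start "no later than 6 hours after randomization".
- Entry limits: Protocol 5.1, criterion 16, excludes systolic pressure below 90 mmHg. The listed criteria set no upper limit.
- Post-infusion rows: Table C-2 has separate criteria here, for systolic pressure "> 160 mm Hg systolic and > 20 mm Hg above pre-infusion value". Their reference is the pre-infusion value, not Baseline.

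**The concern.** Every baseline in this trial is an acute-phase reading, yet it serves as the reference for a year of later readings. If pressure is high in the first hours after the stroke and then settles, a later return to 180 mmHg or more may not be a rise of 20 mmHg from that baseline. A subject whose only readings of 180 or more are of this kind is absent from both the count and the listing for the criterion. In a post-stroke population this table is where a reader looks for marked hypertension by arm. The visible plan has no count against the absolute limit alone.

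**Working it through.** **Inputs from the documents.** Randomization at most 24 h after last known normal (Protocol 5.1); first dose at most 6 h later (SAP 2.2); criterion of at least 180 mmHg and a rise of at least 20 mmHg (Table C-2); about 120 subjects randomized 1:1, so about 60 per arm (Protocol 4.2). The plan states no figure of its own to reproduce on this point.

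**Step 1: age of the baseline.** 24 + 6 = 30 h after last known normal at the latest.

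**Step 2: effective limit.** For baseline B, in whole mmHg, the lowest flagged reading is max(180, B + 20). It exceeds 180 once B is 161 or more.

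| Baseline | Lowest flagged reading | Readings of 180 or more left unflagged |
|---|---|---|
| 160 | 180 | none |
| 165 | 185 | 180–184 |
| 175 | 195 | 180–194 |
| 185 | 205 | 180–204 |
| 200 | 220 | 180–219 |

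**Step 3: which rule binds.** A reading at least 20 above baseline is already more extreme than baseline, so on this row the Protocol 7.4 clause adds nothing to Table C-2. With a bare 180 limit, that clause alone would set the limit at max(180, B + 1) and lose readings only when B is 180 or more.

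**Step 4: how many subjects (illustration).** The documents give no pressure distribution, so all of these are assumptions:
- baseline systolic mean 145 to 165, SD 22 to 25;
- later usual level 138, SD 16, correlated 0.3 or 0.5 with baseline;
- visit-to-visit SD 13;
- 13 later readings (12 at Weeks 4 to 48, plus Week 52).

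Across 400,000 simulated subjects, about 12.5% reach 180 or more at least once. Share missed = 1 − flagged/12.5%.

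| Baseline mean (SD) | P(baseline > 160) | Flagged, correlation 0.3 / 0.5 | Missed, correlation 0.3 / 0.5 |
|---|---|---|---|
| 145 (22) | 25% | 9.2% / 8.1% | 26% / 35% |
| 155 (22) | 41% | 7.1% / 5.6% | 43% / 55% |
| 165 (25) | 58% | 4.8% / 3.2% | 62% / 74% |

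With 60 per arm, about 60 × 0.125 = 7.5 subjects reach 180. Between 60 × 0.032 = 1.9 and 60 × 0.092 = 5.5 of them are flagged.

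A single-visit model with other assumptions (baseline mean 145 to 165, SD 22; later mean 135 to 145, SD 18; correlation 0.2 to 0.4) gives 30% to 87% of readings of 180 or more missed. Such readings are rare there, at 0.7% to 2.8% per visit.

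**Step 5: what this does to a comparison of arms.** Take the Step 4 model, shift the later level in one arm by an assumed +5 or +10 mmHg, and compute z = (p1 − p0) / √[p1(1 − p1)/60 + p0(1 − p0)/60].
- For +5 mmHg, z is about 1.0 on the absolute count and about 0.70 to 0.95 under Table C-2.
- For +10 mmHg, z is about 2.1 on the absolute count and about 1.5 to 2.1 under Table C-2.
- The relative loss of z runs from about 4% (baseline mean 145) to about 31% (baseline mean 165). Simulation error is a point or two.

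**Step 6: the post-infusion rows.** Take a Day 1 baseline of 172, a pre-infusion value of 140 and a post-infusion value of 170. Table C-2 flags it: 170 > 160, and 170 − 140 = 30 > 20. Read literally, the Protocol 7.4 clause would not count it, since 170 < 172.

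**The case against.** The best defense is that requiring a change from baseline is a deliberate and respectable choice. It isolates worsening on treatment and leaves out long-standing hypertension. In the simulation the between-arm risk ratio is in fact larger under Table C-2 than on the absolute count: about 1.6 to 1.8 against 1.5 for +5 mmHg, and 2.4 to 3.1 against 2.2 for +10 mmHg. No safety hypothesis test is planned.

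Other outputs also carry pressure data. Protocol 7.4 states: "Change from baseline to each planned visit and to the minimum, maximum and final value during the Treatment Period will be summarized". SAP 9.4 gives by-visit means and extremes and the pre- to post-infusion change. Protocol 6.1 makes a vital-sign change an adverse event if it leads to discontinuation, needs therapeutic intervention or is judged one by the investigator. A DMC sees unblinded data.

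Much of this stands, and it makes the point a small one. It does not close the gap. By-visit extremes show one value per arm, not how many subjects passed a limit. Change to the maximum uses the same acute baseline. The adverse-event route is conditional.

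Two stronger readings are tempting:
- A reader might blame the more-extreme-than-baseline clause in Protocol 7.4. For systolic-high it is redundant (Step 3).
- A reader might see a real contradiction between Protocol 7.4 and the post-infusion rows. Those rows state their own reference, and Protocol 7.1 leaves complete details to the SAP. One clarifying sentence is enough, although SAP 13.1 reports no change from the Protocol.

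**Conclusion.** The point holds as a cheap improvement. For any baseline above 160 mmHg, Table C-2 leaves a band of later pre-infusion readings, from 180 to just below baseline + 20, uncounted and unlisted. That much follows from the documents alone.

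The size rests on assumed distributions: about 26% to 74% of subjects reaching 180 missed, and about 4% to 31% of the expected between-arm z lost at 60 per arm. The first range should not be read as the loss of signal. The larger z losses occur only at the top of the assumed range for mean baseline.

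A reader might infer that later readings of 180 or more are lost altogether, or that the rule hides a difference between arms. The documents support neither. Readings at or above baseline + 20 are flagged, qualifying post-infusion rises are flagged whatever the baseline, and the rule is identical in both arms. The effect is lost sensitivity without evident bias. Only the systolic row was simulated.

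**What to change.** - In SAP 9.4 and Table C-2, keep the existing flag. Beside it add, by arm and from Week 4 on, a count and a listing of subjects who reach the absolute high limits already in Table C-2, without the change-from-baseline condition. No new threshold is needed.
- Reconcile Protocol 7.4 with the Table C-2 post-infusion rows in one sentence that says whether the baseline clause applies to them, given that the rows use the same-visit pre-infusion value.

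The cost is SAP wording and a few table rows from data already collected. The downside is that background hypertension is counted too. It is balanced between arms only in expectation at about 60 per arm, so the two counts should be read side by side.

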7.5 Interim Analysis

Safety and select efficacy data will be reviewed by an external DMC as described in Section [2.2](#) and Section [6.1](#).

7.6 Multiplicity Adjustment and Overall Type I Error Control

This is a Phase 2a, exploratory, hypothesis-generating study; therefore, there will be no control of Type I error for primary, secondary, or exploratory analyses for this study.

7.7 Sample Size Determination

The primary efficacy endpoint is the monthly-adjusted, model-based AUC of the NIHSS total score during the Treatment Period. Approximately [REDACTED] subjects will be randomized to elezanumab [REDACTED] mg or placebo in a [REDACTED] ratio. Assuming a true difference in AUC of [REDACTED], this sample size is sufficient to show a [REDACTED] difference in AUC between treatment and placebo with a posterior probability greater than [REDACTED]%. This sample size was calculated based on simulations and included a [REDACTED] % mortality rate for the population under [REDACTED] years of age, [REDACTED] % mortality rate for the population greater than or equal to [REDACTED] years of age, and an additional [REDACTED] % dropout rate.

The number and proportion of missing assessments (due to missed visits or study drug discontinuation) will be monitored on an ongoing basis and, if the proportion of missing assessments is higher than planned, additional subjects may be added.

8 ETHICS

8.1 Independent Ethics Committee/Institutional Review Board

The protocol, informed consent form(s), recruitment materials, and all subject materials will be submitted to the IEC/IRB for review and approval. Approval of both the protocol and the informed consent form(s) must be obtained before any subject is enrolled at that site. Any amendment to the protocol will require review and approval by the IEC/IRB before the changes are implemented to the study. In addition, all changes to the consent form(s) will be IEC/IRB approved.

8.2 Ethical Conduct of the Study

The study will be conducted in accordance with the protocol, Operations Manual, International Council for Harmonisation of Technical Requirements for Pharmaceuticals for Human Use (ICH) guidelines, applicable regulations, and guidelines governing clinical study conduct and the ethical principles that have their origin in the Declaration of Helsinki. Responsibilities of the investigator are specified in [Appendix B](#).

In the event a significant disaster/crisis (e.g., epidemic/pandemic, natural disaster, conflict/combat) occurs leading to difficulties in performing protocol-specified procedures, AbbVie may engage with study site personnel in efforts to ensure the safety of subjects, maintain protocol compliance, and minimize risks to the integrity of the study while trying to best manage subject continuity of care. This may include alternative methods for assessments (e.g., phone contacts or virtual site visits), alternative locations for data collection (e.g., use of a local lab instead of a central lab), and shipping investigational product and/or supplies directly to subjects to ensure continuity of treatment where allowed. In all cases, these alternative measures must be allowed by local regulations and permitted by IRB/IEC. Investigators must notify AbbVie if any urgent safety measures are taken to protect the subjects against any immediate hazard.

8.3 Subject Confidentiality

To protect subjects' confidentiality, all subjects and their associated samples will be assigned numerical study identifiers or "codes." No identifiable information will be provided to AbbVie.

9 SOURCE DOCUMENTS AND CASE REPORT FORM COMPLETION

The investigator is responsible for ensuring the accuracy, completeness, legibility, and timeliness of the data reported. All source documents must be attributable, legible, contemporaneous, original, accurate, and complete to ensure accurate interpretation of data. Clinical site monitoring is conducted to ensure that the rights and well-being of human subjects are protected, that the reported trial data are accurate, complete, and verifiable, and that the conduct of the trial is in compliance with the currently approved protocol, ICH Good Clinical Practice (GCP), and applicable local regulatory requirement(s). During the COVID-19 pandemic, remote monitoring of data may be employed if allowed by the local regulatory authority, IRB/IEC, and the study site.

10 DATA QUALITY ASSURANCE

AbbVie will ensure that the clinical trial is conducted with a quality management system that will define quality tolerance limits in order to ensure human subject protection and reliability of study results. Data will be generated, documented, and reported in compliance with the protocol, ICH GCP, and applicable regulatory requirements.

11 COMPLETION OF THE STUDY

The end-of-study is defined as the date of the last subject's last visit.

APPENDIX A. STUDY-SPECIFIC ABBREVIATIONS AND TERMS

Abbreviation	Definition
ADA	anti-drug antibody
AE	adverse event
AESI	adverse events of special interest
ASPECTS	Alberta Stroke Program Early CT Score
ATEMS	AbbVie Temperature Excursion Management System
AUC	area under the curve
BI	Barthel Index
BDI-II	Beck Depression Inventory-II
BMP	bone morphogenetic protein
COVID-19	Coronavirus disease – 2019
CS	clinically significant
CSF	cerebrospinal fluid
C-SSRS	Columbia-Suicide Severity Rating Scale
CT	computed tomography
DMC	data monitoring committee
DTP	direct-to-patient
DWI	diffusion-weighted imaging
EC	ethics committee
ECG	electrocardiogram
eCRF	electronic case report form
EQ-5D-5L	EuroQol 5 Dimensions 5 Levels Health State Instrument
EVT	endovascular therapy
FAS	full analysis set
FSH	follicle-stimulating hormone
GCP	Good Clinical Practice
GGT	gamma glutamyl transferase
GLP	Good Laboratory Practice
IB	Investigator's Brochure
ICH	International Council for Harmonisation of Technical Requirements for Pharmaceuticals for Human Use
IEC	Independent Ethics Committee

Ig	immunoglobulin
IL-10	interleukin-10
IL-6	interleukin-6
IMP	investigational medicinal product
INR	international normalized ratio
IRB	Institutional Review Board
IRT	interactive response technology
IU	international unit
IUD	intrauterine device
IUS	intrauterine hormone-releasing system
IV	intravenous
LDH	lactate dehydrogenase
MedDRA	Medical Dictionary for Regulatory Activities
MMIA	minimal missed infusion analysis
MMP-9	matrix metalloproteinase-9
MMRM	mixed effects model with repeated measures
MoCA	Montreal Cognitive Assessment
MRI	magnetic resonance imaging
mRS	Modified Rankin Scale
MS	multiple sclerosis
MT	magnetization transfer
mTICI	modified thrombolysis in cerebral infarction
nAb	neutralizing antibody
NCS	not clinically significant
NfL	neurofilament light chain
NIHSS	National Institutes of Health Stroke Scale
PCS	potentially clinically significant
PD visit	Premature Discontinuation visit
pMCAO	permanent middle cerebral artery occlusion
PK	pharmacokinetic(s)
PRO	patient-reported outcome
PT	Preferred Term
RGMa	Repulsive guidance molecule A
RSI	Reference Safety Information

SAE	serious adverse event
SAP	statistical analysis plan
SAR	serious adverse reaction
SIS-16	Stroke Impact Scale-16
SOC	System Organ Class
SUSAR	suspected unexpected serious adverse reactions
TIA	transient ischemic attack
TOAST	Trial of ORG 10172 in Acute Stroke Treatment
tPA	tissue plasminogen activator

